6.6 DOSE MODIFICATION

6.6.1 Doublet cohort - Part 1 (Safety Run-In)

If ≥ 2 of the first 3 patients or of the 6 patients treated at the initial DL present with DLTs, the SC may decide to decrease the dose of tusamitamab ravidansine to DL -1 (80 mg/m² in combination with 8 mg/kg ramucirumab). The tolerability of the reduced DL will be assessed in at least 6 participants. Dose reduction in the case of 2 or more DLTs for the cohort is shown in [Table 9](#).

Table 9 - Dose reduction for doublet cohort for Part 1 (safety run-in)

Dose level (DL)	tusamitamab rfvantsine	Ramucirumab
Starting dose	100 mg/m ² Q2W	8 mg/kg Q2W
Minus -1 (DL-1)	80 mg/m ² Q2W	8 mg/kg Q2W

BSA=body surface area; DL=dose level; Q2W=every 2 weeks.

Infusion of tusamitamab rfvantsine will be administered at least 1 hour after the end of ramucirumab infusion. For patients with a BSA >2.20 m², the tusamitamab rfvantsine dose will be calculated based on a BSA of 2.20 m².

6.6.2 Triplet cohort

If ≥ 2 of the first 3 patients or of the 6 patients treated at the initial DL present with DLTs, the SC may decide to decrease the dose of tusamitamab rfvantsine to DL -1 (120 mg/m² in combination with 10 mg/kg ramucirumab). The tolerability of the reduced DL will be assessed in at least 6 participants. Dose reduction in the case of 2 or more DLTs for the cohort is shown in [Table 10](#).

Table 10 - Dose reduction for triplet cohort

Dose level (DL)	tusamitamab rfvantsine	ramucirumab	pembrolizumab
Starting dose	150 mg/m ² Q3W	10 mg/kg Q3W	200 mg Q3W
Minus -1 (DL-1)	120 mg/m ² Q3W	10 mg/kg Q3W	200 mg Q3W

DL=dose level; Q3W=every 3 weeks.

Infusion of tusamitamab rfvantsine will be administered at least 1 hour after the end of ramucirumab infusion. For patients with a BSA >2.20 m², the tusamitamab rfvantsine dose will be calculated based on a BSA of 2.20 m².

6.6.3 Doublet cohort (Part 1 and Part 2) and triplet cohort: Requirements for retreatment

For the retreatment of patients on Day 1 of each subsequent cycle, the following conditions should be met:

- Neutrophils count $\geq 1.5 \times 10^9/L$.
- Platelets $\geq 100 \times 10^9/L$.
- Total bilirubin $\leq 1.5 \times ULN$.
- AST, ALT $\leq 2.5 \times ULN$ or $\leq 5 \times ULN$ in case of documented liver metastasis.
- No IMP-related toxicity Grade >1 (except for alopecia) or baseline severity.
- Urine protein:
 - $<2+$ on dipstick or urinalysis for C1D1,
 - $\leq 2+$ on dipstick or urinalysis for subsequent infusions,
 - OR
 - <2 g on 24 hours urine collection.
- Hypertension is controlled, every attempt should be made to control blood pressure (<140 mmHg systolic and <90 mmHg diastolic).
- Wound healing: any wound is fully healed.

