The starting dose for tusamitamab ravidansine is 150 mg/m² and was defined based on findings from first-in-human study TED13751. In this study, the RP2D for tusamitamab ravidansine given Q3W was 170 mg/m². Given that tusamitamab ravidansine exposure PK parameters at Cycle 1 of administration as a single agent of 170 mg/m² Q2W were significantly associated with the

occurrence of Grade ≥ 2 corneal events, it is anticipated that 150 mg/m² may result in less ocular toxicity, and overall will be better tolerated than 170 mg/m². In addition, this dose corresponds to the same dose intensity as with the recommended 100 mg/m² Q2W dose.

A minimum delay of 1 week is required between the initial dose in the first participant treated in a DL cohort and dosing the next 2 participants treated at the same DL.

- If $\leq 1/3$ participants treated at the starting dose experiences a DLT, 3 additional participants will be treated to confirm the tolerability of the combination.
 - If $\leq 1/6$ participants treated at the starting dose experiences a DLT, the starting dose will be the RP2D.
 - If $\geq 2/6$ participants treated at the starting dose experience DLTs, the dose will be de-escalated to DL -1.
- If $\geq 2/3$ participants treated at the starting dose experience DLTs, the dose will be de-escalated to DL minus 1 (DL -1).
- If ≤ 1 of the first 3 participants treated at DL -1 experiences a DLT, 3 additional participants will be treated at this DL.
 - If $\leq 1/6$ participants treated at DL -1 experiences a DLT, DL-1 will be the RP2D.
 - If $\geq 2/6$ participants treated at DL -1 experience a DLT, an alternative dosage might be considered or the triplet cohort may be stopped.
- If $\geq 2/3$ participants treated at DL -1 experience a DLT, an alternative dosage might be considered or the triplet cohort may be stopped.

Note: If $\geq 2/6$ or $\geq 2/3$ participants treated at DL -1 experience DLTs, an alternative dosage might be considered from a safety viewpoint by the Sponsor after consulting the Study Committee (SC).

Table 2 shows dose reduction in the case of DLTs occurring in 2 or more of the first 3 participants or of 6 participants in a DL triplet cohort. **Figure 2** shows the decision tree for doses to be administered.

[figure not shown]
Table 2 - Dose reduction for the triplet cohort

Dose level (DL)	Tusamitamab rfvansine	ramucirumab	pembrolizumab
Starting dose	150 mg/m ² Q3W	10 mg/kg Q3W	200 mg Q3W
Minus -1 (DL-1)	120 mg/m ² Q3W	10 mg/kg Q3W	200 mg Q3W

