 - In the triplet cohort, tusamitamab ravtansine 150 mg/m² (or 120 mg/m², if deemed the appropriate dose by the SC) will be administered via IV infusion over 1 hour, 30 minutes on Day 1, and then every 3 weeks.
- For patients with a body surface area (BSA) >2.20 m², the dose of tusamitamab ravtansine will be calculated based on a BSA of 2.20 m².

Pembrolizumab

In the triplet cohort, pembrolizumab will be administered after ramucirumab and tusamitamab ravtansine.

- Formulation: Keytruda® (pembrolizumab) is a concentrate for solution for infusion supplied in 100 mg/4 mL (25 mg/mL) solution in single-dose vials.
- Route of administration: intravenous (IV) infusion.
- Dose regimen: pembrolizumab will be administered as a 200 mg IV infusion over 30 minutes on Day 1 and then Q3W.

Noninvestigational medicinal products:

Premedication:

Both tusamitamab ravtansine and ramucirumab have potential risk of infusion-related allergic reaction; therefore, premedication with an IV histamine H1 antagonist (diphenhydramine 50 mg IV or equivalent; eg, cetirizine, promethazine, dexchlorpheniramine, according to local approval and availability) given approximately at least 15 minutes before ramucirumab administration is required for all participants. If a participant previously experienced an infusion-related reaction (IRR) following a dose of ramucirumab or tusamitamab ravtansine, premedication for subsequent infusions will also include dexamethasone 10 mg IV and acetaminophen (paracetamol). All drugs used as premedication will be entered on the concomitant premedication page.

Statistical considerations:

- **Sample size calculations:**

This study is divided into 2 cohorts:

Doublet cohort: the cohort is divided in 2 parts: a safety run-in (Part 1) and Part 2. In the safety run-in Part, 6 to 12 DLT-evaluable participants will be enrolled in order to confirm the RP2D. In Part 2, the plan is to enroll and treat enough participants to attain a total of 30 participants evaluable for activity (ie, having at least 1 post-baseline tumor assessment). The 6 participants treated at the RP2D will also be evaluable for Part 2.

Triplet cohort: the cohort will have only 1 part: a safety run-in. 6 to 12 DLT-evaluable participants will be enrolled in order to confirm the RP2D.

- **Main analysis populations:**

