Infusion of tusamitamab rfvansine will be administered at least 1 hour after the end of ramucirumab infusion. For patients with a BSA >2.20 m², the tusamitamab rfvansine dose will be calculated based on a BSA of 2.20 m².

The decision tree for doses in Part 1 is summarized in [Figure 4](#).

Figure 4 - Decision tree for the doublet cohort Part 1 for tusamitamab ravtansine

*Note: In case of 2 or more DLTs at DL -1, the cohort may be stopped or the dosage reconsidered.

Abbreviations: DL -1=dose level -1 (80 mg/m²); DLT=dose-limiting toxicity; RP2D=recommended dose.

Following the identification of the RP2D, Part 2 of the study will be initiated.

Dose limiting toxicity definition

All AEs specified in [Table 5](#) occurring during the first 2 cycles of treatment, unless due to disease progression or to a cause obviously unrelated to IMP, will be considered DLTs. The duration of the DLT observation period will be longer for a participant who delays initiation of Cycle 2 due to a treatment-related AE for which the event's duration would determine whether the AE meets the definition of a DLT. The NCI CTCAE version 5.0 will be used to assess the severity of AEs. Causal relationships are to be determined by the Investigator. The DLTs will be confirmed by the SC.

Table 5 - Dose-limiting toxicities

Hematological abnormalities
Grade 4 neutropenia for 7 or more consecutive days
Grade 3 to 4 neutropenia complicated by fever (temperature $\geq 38.5^{\circ}\text{C}$ on more than 1 occasion) or microbiologically or radiographically documented infection
Grade ≥ 3 thrombocytopenia associated with clinically significant bleeding requiring clinical intervention
Non-hematological abnormalities
Elevated urine protein ≥ 3 g/24 h
Grade 4 non-hematologic AE
Grade ≥ 3 keratopathy
Grade 4 or refractory hypertension
In addition, any other AE that the recruiting Investigators and Sponsor deem to be dose limiting, regardless of its grade, may also be considered as DLT.

Part 2: It is planned that 30 treated patients will be evaluable for response (the 6 patients from the safety run-in treated at the recommended dose will be included). During the treatment period, participants will have tumor assessments every 8 weeks.

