The DLT observation period is the first cycle (approximately 21 days). A DLT-evaluable participant must have completed 1 cycle of treatment or have been discontinued from study treatment because of a DLT. DLT non-evaluable participants will be replaced.

A minimum delay of 1 week is required between the initial dose in the first participant treated in a DL cohort and dosing the next 2 participants treated at the same DL.

- If $\leq 1/3$ participants treated at the starting dose experiences a DLT, 3 additional participants will be treated to confirm the tolerability of the combination.
 - If $\leq 1/6$ participants treated at the starting dose experiences a DLT, the starting dose will be the RP2D.
 - If $\geq 2/6$ participants treated at the starting dose experience DLTs, the dose will be de-escalated to DL -1.
- If $\geq 2/3$ participants treated at the starting dose experience DLTs, the dose will be de-escalated to DL minus 1 (DL -1).
 - If $\leq 1/6$ participants treated at DL -1 experiences a DLT, DL-1 will be the RP2D.
 - If $\geq 2/6$ participants treated at DL -1 experience a DLT, an alternative dosage might be considered or the triplet cohort may be stopped.
- If $\geq 2/3$ participants treated at DL -1 experience a DLT, an alternative dosage might be considered or the triplet cohort may be stopped.

Note: if $\geq 2/6$ or $\geq 2/3$ participants treated at DL -1 experience DLTs, an alternative dosage might be considered from a safety viewpoint by the Sponsor after consulting with SC. Dose reduction is shown in [Table 6](#).

Table 6 - Dose reduction for the triplet cohort

[figure not shown]
Dose level (DL)	tusamitamab ravidansine	ramucirumab	pembrolizumab
Starting dose	150 mg/m ² Q3W	10 mg/kg Q3W	200 mg Q3W
Minus -1 (DL-1)	120 mg/m ² Q3W	10 mg/kg Q3W	200 mg Q3W

DL=dose level; Q3W=every 3 weeks.

Infusion of tusamitamab ravidansine will be administered at least 1 hour after the end of ramucirumab infusion. For patients with a BSA >2.20 m², the tusamitamab ravidansine dose will be calculated based on a BSA of 2.20 m².

The decision tree for doses for triplet cohort is summarized in [Figure 5](#).

Figure 5 - Decision tree for the triplet cohort for tusamitamab ravidansine

*Note: In case of 2 or more DLTs at DL -1, the cohort may be stopped or the dosage reconsidered.

Abbreviations: DL -1=dose level -1 (120 mg/m²); DLT=dose-limiting toxicity; RP2D=recommended dose.

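### With two or more DLTs at the starting dose, de-escalation is mandatory in the Synopsis and Section 4.1 but discretionary in Sections 6.6.1 and 6.6.2, and nothing says which governs

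*Protocol*

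**What the plan says.** The trigger is the same everywhere: at least 2 of the first 3, or at least 2 of 6, participants with DLTs at the starting dose. The stated consequence differs.

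- **Mandatory.** Section 4.1, in its at-least-2-of-6 bullet: "participants treated at the starting dose experience DLTs, the dose will be de-escalated to DL -1". The at-least-2-of-3 bullet has the same force. Both bullets appear for both cohorts, in the Synopsis and in Section 4.1.
- **Discretionary.** Section 6.6.2 (triplet): "the SC may decide to decrease the dose of tusamitamab rfvantsine to DL -1". Section 6.6.1 (doublet): "the SC may decide to decrease the dose of tusamitamab", with DL -1 as the destination.

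Other places give the SC a role without settling the matter. The DLT definition in Section 4.1 says "The DLTs will be confirmed by the SC". The Synopsis dose regimen gives the lower dose as applying "if deemed the appropriate dose by the SC". Section 10.1.5 places decisions to continue or reduce after SC review.

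On the number treated at DL -1, Sections 6.6.1 and 6.6.2 say without condition: "The tolerability of the reduced DL will be assessed in at least 6 participants". The Synopsis adds participants only if at most 1 "of the first 3 participants treated at DL -1 experiences a DLT, 3 additional participants will be treated at this DL". If at least 2 of 3 have DLTs there, Section 4.1 says for the triplet: "participants treated at DL -1 experience a DLT, an alternative dosage might be considered or the triplet cohort may be stopped".

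**The concern.** A de-escalation rule exists so that the response to a toxicity signal is fixed before the signal is seen. Here one observation leads to an obligation in one section and an option in another. Someone following Section 4.1 must lower the dose. Someone following Section 6.6.2 may leave it unchanged and still comply with the words on the page.

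The written rule carries extra weight because there is no data monitoring committee (Section 9.6), and the SC consists of investigators or designees and sponsor staff, with outside experts only ad hoc (Section 10.1.5). The practical target is the triplet cohort, which had not started when SAP version 2.0 was written (SAP Section 1.1). That SAP excludes the triplet, so it cannot resolve the conflict. The doublet run-in appears to be over: Section 4.3 draws on doublet experience and Section 9.2 uses its screening rates. Editing Section 6.6.1 is therefore for consistency only.

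**Working it through.** **1. The plan's own figure.** Section 9.2.3 expects 6 to 12 DLT-evaluable participants in the triplet. The paths in the Synopsis and Section 4.1 are:

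- starting dose accepted: 6;
- starting dose left after 3, then 3 or 6 at DL -1: 3 + 3 = 6 or 3 + 6 = 9;
- starting dose left after 6, then 3 or 6 at DL -1: 6 + 3 = 9 or 6 + 6 = 12.

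The totals are 6, 9 or 12, which reproduces the stated range. Reading Section 6.6.2 as always 6 at DL -1 gives 6, 3 + 6 = 9 or 6 + 6 = 12, which is the same range.

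**2. Can a starting dose with at least 2 DLTs become the recommended dose?** No. The Synopsis and Section 4.1 both require at most 1 DLT in 6, and Section 6.6 does not alter that.

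**3. How often the conflicting text would apply.** DLTs are counted cumulatively, so 2 among the first 3 are already 2 among 6 whatever the next 3 would have shown. Meeting either limb of the trigger is therefore the event of at least 2 DLTs in 6:

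P(trigger) = 1 − (1−p)^6 − 6p(1−p)^5.

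The documents give no value for the true DLT rate p. The values below are assumptions.

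| Assumed p | (1−p)^6 | 6p(1−p)^5 | P(trigger) |
|---|---|---|---|
| 10% | 0.531441 | 0.354294 | 11.4% |
| 20% | 0.262144 | 0.393216 | 34.5% |
| 30% | 0.117649 | 0.302526 | 58.0% |
| 40% | 0.046656 | 0.186624 | 76.7% |

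**4. The secondary point at DL -1.** The unconditional 6 in Section 6.6.2 meets the 2-of-3 provision in Section 4.1 only if the dose was de-escalated and then at least 2 of the first 3 at DL -1 have DLTs. The second step has probability 3p²(1−p) + p³ = 2.8%, 10.4%, 21.6% and 35.2%. With the same assumed rate at both levels, the joint probabilities are:

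- 10%: 0.114265 × 0.028 = 0.3%
- 20%: 0.344640 × 0.104 = 3.6%
- 30%: 0.579825 × 0.216 = 12.5%
- 40%: 0.766720 × 0.352 = 27.0%

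Equal rates are a further assumption; a lower rate at the reduced dose would make these smaller.

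**5. Does another clause break the tie?** Section 6.6.4 says to follow the most conservative adjustment when recommendations conflict, but it concerns a single participant with several adverse reactions, not a cohort rule. No other passage ranks the two wordings.

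**The case against.** The best defence is that the sections do different jobs: Section 4.1 states the outcome, and Section 6.6 names the body that acts. The trigger already needs an SC step, because the SC confirms DLTs, and Section 10.1.5 puts the SC before any decision to continue or reduce. That reading is possible, but a sentence that only named the actor would not need a permissive verb. As written, it also allows the dose not to be reduced.

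The defence is right on several stronger readings that a reader might infer.

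- **That Section 6.6.2 permits 3 more participants at a failed starting dose.** It authorises none. The only written route from 3 to 6 there is at most 1 DLT in the first 3. Discretion could equally be used to stop the cohort, which is the safer course.
- **That Section 4.1 ends DL -1 at 3 participants while Section 6.6.2 forces 6, so totals are 6 against 9 or 9 against 12.** Section 4.1 is itself permissive at that point, so those totals treat an option as a hard stop. The 6 in Section 6.6.2 can mean the number needed to apply the at-most-1-in-6 criterion.
- **That the triplet text of Section 4.1 changes the rule by omitting the step from 3 to 6 at DL -1.** The Synopsis has the step, the at-most-1-in-6 rule implies it, and the Figure 5 decision tree is not visible in the text reviewed. It merits a note only.

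Other safeguards also stand. DLTs are events of special interest (Section 8.3.1) reported within 24 hours (Section 8.3.2), the SC meets about every 2 weeks, and the first participant at a level is dosed at least a week ahead of the next two.

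**Conclusion.** The conflict at the starting dose is real in both cohorts and worth correcting. Its consequence is an ambiguous safety rule. No recommended-dose criterion, sample size or estimand is affected.

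The trigger probabilities of 11.4% to 76.7% rest entirely on assumed DLT rates of 10% to 40%. Sections 2.3 and 4.3 describe tusamitamab ravtansine at 150 mg/m² with pembrolizumab, without ramucirumab, as well tolerated, so the documents lend no support to the upper rates. The mismatch over numbers at DL -1 is secondary, since both texts can be read together. The Synopsis dose-regimen wording is compatible with either rule and needs no edit.

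**What to change.** Before the first triplet dose, amend Section 6.6.2, and Section 6.6.1 for consistency.

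1. Replace the discretionary clause with: *once the SC has confirmed the DLTs, no further participants will be started at the initial DL and the dose will be decreased to DL -1, unless the cohort is stopped*. This keeps the SC's confirming role and leaves stopping open.
2. As a secondary alignment, replace the sentence on numbers at the reduced level with: *6 DLT-evaluable participants are needed to declare DL -1 the RP2D; enrolment at DL -1 goes from 3 to 6 only if at most 1 of the first 3 has a DLT, otherwise Section 4.1 applies*. This adds no hard stop beyond what Section 4.1 states.

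The cost is protocol wording. The SC gives up discretion to keep enrolling at a starting dose with 2 or more DLTs, which Section 4.1 already withholds.

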Event	Symptoms severity (Nadir) (NCI CTCAE v5)	Management of IMP dosing (ramucirumab)	Management of IMP dosing (tusamitamab rfvansine)	Supportive care guidelines
Febrile neutropenia	Grade 3 Absolute neutrophil count <1000/mm ³ with a single temperature of >38.3°C (101°F) or a sustained temperature of ≥38°C (100.4°F) for more than 1 hour	Delay cycle until absolute neutrophil count >1500/mm ³ . 1st episode administer next cycle at the same dose and administer G-CSF 2nd episode: administer ramucirumab at reduce dose 3rd episode: definitive discontinuation	Delay cycle until absolute neutrophil count >1500/mm ³ . 1st episode administer next cycle at the same dose and administer G-CSF 2nd episode: administer tusamitamab rfvansine at reduce dose 3rd episode: definitive discontinuation	To ensure relative dose intensity, G-CSF is recommended as secondary prophylaxis in all patients with Grade 3 febrile neutropenia ASCO guideline is recommended for supportive treatment if there are no defined clinical standards (23)
	Grade 4 Life-threatening consequences	Administration changes to be decided at the Investigator's discretion per product label	Administration changes to be decided at the Investigator's discretion. 1st episode: administer next cycle at reduced dose and administer G-CSF 2nd episode: definitive discontinuation	
Hypertension	Grade 3 Severe hypertension	Withhold ramucirumab until controlled with medical management, and restart at same dose	Administer tusamitamab rfvansine as planned	
	Grade 4 Severe hypertension that cannot be controlled with antihypertensive therapy	Definitively discontinue ramucirumab	Administer tusamitamab rfvansine as planned	
Proteinuria	First occurrence of increased urine protein levels greater than or equal to 2 g per 24 hours	Omit ramucirumab until urine protein level is ≤2 g per 24 hours; then resume ramucirumab at a reduced dose (in doublet cohort, 8 mg at 1st episode, then 5 mg if 2nd episode and in triplet cohort, 8 mg at 1 st episode, then 6 mg if 2d episode)	Administer tusamitamab rfvansine as planned	
	Reoccurrence of urine protein level greater than 2 g per 24 hours following initial dose reduction	Omit ramucirumab until protein level is ≤2 g per 24 hours; then resume ramucirumab at a reduced dose:(6 mg or 5 mg)	Administer tusamitamab rfvansine as planned	

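### The Day 1 retreatment conditions in Protocol 6.6.3 name no drug, so with persisting proteinuria, uncontrolled hypertension or toxicity above Grade 1 they can contradict the drug-by-drug instructions in Appendix 4

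*Protocol*

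**What the plan says.** Protocol 6.6.3 covers both cohorts. It begins "For the retreatment of patients on Day 1 of each subsequent cycle, the following conditions should be met" and does not split the conditions by drug. Three of them matter here.

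- Urine protein: 2+ or less "on dipstick or urinalysis for subsequent infusions", or else below 2 g on a 24 h collection. The two branches are joined by OR.
- Blood pressure: "Hypertension is controlled, every attempt should be made to control blood pressure", with a target below 140/90 mmHg.
- Toxicity: "No IMP-related toxicity Grade >1 (except for alopecia) or baseline severity".

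Appendix 4 (section 10.4) has separate columns for ramucirumab and tusamitamab ravtansine.

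- Proteinuria: the row "First occurrence of increased urine protein levels greater than or equal to 2 g per 24 hours" omits ramucirumab and tells the site "Administer tusamitamab rfvansine as planned". The recurrence row does the same. Above 3 g/24 h, or with nephrotic syndrome, ramucirumab stops and tusamitamab ravtansine becomes a benefit/risk decision.
- Grade 3 hypertension: "Withhold ramucirumab until controlled with medical management, and restart at same dose". Tusamitamab ravtansine is given.
- Grade 4 hypertension, described as "Severe hypertension that cannot be controlled with antihypertensive therapy": ramucirumab stops for good. Tusamitamab ravtansine is given.

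Section 8.2.6.7 and footnote k of both study flow charts call for a 24 h collection once the dipstick reaches 2+. Section 8.2.6.7 then withholds ramucirumab at 2 g or more. Section 6.6.4 refers toxicity handling to Appendix 4 and allows the remaining drugs to continue when one is permanently stopped.

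**The concern.** A site deciding on Day 1 whether to dose can get two answers from the same protocol. The first conflict is over tusamitamab ravtansine: the only problem may be one that the protocol manages by holding ramucirumab, yet 6.6.3 read literally holds everything. The second is over ramucirumab: a site using 6.6.3 as its checklist could tick the urine item on a 2+ dipstick although the 24 h result calls for withholding.

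The stake is uneven dosing between sites and, for ramucirumab, a checklist item that points the wrong way. The doublet exposure tables would also be affected. SAP 4.7.1.1 counts cycle delays, while 4.7.1.2 and 4.7.1.3 count delays and omissions per drug. The same event could therefore appear as a delayed cycle at one site and as an omitted ramucirumab dose at another.

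**Working it through.** The plan states no figure to reproduce, so the check sets the rules side by side.

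**Urine protein, cycles after the first.** The 6.6.3 item passes if (dipstick 2+ or less) OR (24 h protein below 2 g). Appendix 4 acts on the 24 h result. The grid takes the dipstick values that require a collection, without nephrotic syndrome. T = tusamitamab ravtansine, R = ramucirumab.

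| Dipstick | 24 h protein | 6.6.3 urine item | Appendix 4 | Result |
|---|---|---|---|---|
| 2+ | below 2 g | pass | no action | agree |
| 2+ | 2 to 3 g | pass (dipstick) | omit R, give T | differ on R |
| 2+ | above 3 g | pass (dipstick) | stop R; T by benefit/risk | differ on R |
| above 2+ | below 2 g | pass (24 h) | no action | agree |
| above 2+ | 2 to 3 g | fail | omit R, give T | differ on T |
| above 2+ | above 3 g | fail | stop R; T by benefit/risk | no direct conflict |

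So 1 + 2 = 3 of 6 cells differ: one on tusamitamab ravtansine and two on ramucirumab. The grid scores the urine item alone, not the whole of 6.6.3.

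**Hypertension.** The 6.6.3 condition fails if blood pressure is uncontrolled on Day 1. Where the Grade 3 or Grade 4 row applies at that time, Appendix 4 still gives tusamitamab ravtansine. If Grade 3 hypertension has been brought under control by Day 1, 6.6.3 passes and the two agree.

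**Toxicity above Grade 1.** These Appendix 4 rows give one drug as planned for an event that is, or can be, above Grade 1:

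- ramucirumab given: keratopathy Grades 2, 3 and 4 (3); conduction disorder Grade 2 or more (1); peripheral neuropathy Grades 3 and 4 (2)
- tusamitamab ravtansine given: hypertension Grades 3 and 4 (2); arterial thromboembolic events, listed for all grades (1)

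Total: 3 + 1 + 2 + 2 + 1 = 9 rows. The severity column is headed as a nadir, and 6.6.4 adjusts on the worst grade within a cycle, whereas 6.6.3 looks at Day 1. A row therefore conflicts only if the drug-related event is still above Grade 1, and above baseline severity, on Day 1.

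**Precedence.** Section 6.6.4 sends toxicity handling to Appendix 4 but does not lift the 6.6.3 conditions. Its rule to take the most conservative adjustment is written for a participant with more than one adverse reaction, not for two sections that disagree about one.

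**Details in the Appendix 4 proteinuria rows.** Ramucirumab resumes at 2 g or less, but 8.2.6.7 requires less than 2 g. The first reduced dose for the doublet is given as 8 mg, but in Table 11 8 mg/kg is the starting dose and 6 mg/kg the first reduction.

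**The case against.** The strongest reply is that the intent can be recovered. Section 6.6.4 refers toxicity to Appendix 4, 8.2.6 does the same for adverse event management, and drug-specific text is ordinarily read over a general list. Holding tusamitamab ravtansine by mistake is also the cautious error. For ramucirumab, footnote k prompts the 24 h collection, 8.2.6.7 withholds at 2 g or more, and Appendix 4 omits the dose. A site would have to disregard these to give it at a known 2 g or more. Much of this stands and keeps the point minor. It does not supply the missing precedence sentence.

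Four stronger readings are tempting, and the documents do not support them.

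- A reader might infer that any Grade 3 or 4 hypertension bars all drugs. It does so only while blood pressure is uncontrolled on Day 1.
- A reader might infer that for Grade 4 hypertension the 6.6.3 condition can never be met. Ramucirumab is stopped at that point, and nothing says that blood pressure stays uncontrolled afterwards.
- A reader might infer that the OR clears ramucirumab through 6.6.3. It clears only the urine item; the Grade >1 line may still block dosing. The documents give no grade cut-offs for proteinuria, so that is not settled.
- A reader might infer that a blanket statement that Appendix 4 prevails would settle everything. It would entrench the resume limit and the 8 mg dose noted above.

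**Conclusion.** The inconsistency is real and confined to wording. It arises in three Day 1 situations:

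- dipstick above 2+ with 2 to 3 g/24 h and no nephrotic syndrome, or hypertension still uncontrolled with a Grade 3 or 4 row applying: 6.6.3 bars tusamitamab ravtansine and Appendix 4 gives it;
- dipstick 2+ with 2 g/24 h or more: the urine item passes, while 8.2.6.7 and Appendix 4 withhold or stop ramucirumab;
- a drug-related event still above Grade 1 and above baseline severity: the Grade >1 line can conflict with up to nine Appendix 4 rows.

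The second is a contradictory checklist item, not a missing safeguard. The conclusion rests on reading 6.6.3 as written, for the patient and not for each drug. The documents do not say how often any of these situations would occur. No endpoint definition or planned analysis is wrong because of it.

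**What to change.** In 6.6.3:

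- make the urine-protein and hypertension lines conditions for ramucirumab only;
- require less than 2 g/24 h for ramucirumab whenever the dipstick is 2+ or more, with the 24 h result overriding the dipstick;
- add that where Appendix 4 gives a drug-specific instruction for an event, that instruction decides which drug is held or given on Day 1.

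In the Appendix 4 proteinuria rows, change the resume limit from 2 g or less to less than 2 g, and the first reduced ramucirumab dose for the doublet from 8 mg to 6 mg/kg. They then match 8.2.6.7 and Table 11.

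The added sentence settles only the drugs on which Appendix 4 speaks. Its pembrolizumab table has no keratopathy, neuropathy or conduction row, so in the triplet cohort the Grade >1 line would still govern pembrolizumab for those events.

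Deleting the C1D1 line is optional tidying: it does not belong in a list for later cycles, and exclusion criterion E30 already covers the first dose.

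The cost is a few lines of protocol text. Data collection and analysis do not change.
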